8.1.2 PSYCHOLOGICAL MEASURES

The following measures capture different aspects of psychological functioning including perceptions of cognitive impairment, mood and social participation. Psychological and social distress are known to influence performance on cognitive tests over and above that of any effects of POCD (e.g. Kizilbash, A. H., Vanderploeg, R. D., & Curtiss, G. (2002). Including these variables allows us to control for their influence in statistical analysis. There is evidence of increased risk of social disconnection when people face life changes and periods of vulnerability (Jones et al., 2011; Jetten, Haslam & Haslam, 2012). Surgery involves a period of such vulnerability, which is why two very brief validated measures of this construct are included within the study (i.e., n=3 items). These have the capacity to be delivered face-to-face or online using iPad that will be provided.

European Brain Injury Questionnaire (EBIQ) (10-15 minutes)- The European Brain Injury Questionnaire (EBIQ), is a self-report and relative-report measure of the subjective experience of cognitive, emotional and social difficulties experienced by people with any form of acquired brain injury (Teasdale et al., 1997). It is a clinically reliable measure that assesses change in subjective concerns in these areas over time (Sopena et al., 1997). In the present study it will serve as a subjective index of cognitive change. The measure comprises 66 items rated on a 3-point scale (1=not at all to 3=a lot).

Depression Anxiety and Stress Scale-21 (DASS-21; 3 minutes) - Depression, anxiety and stress both pre- and post- surgery have been shown to hinder recovery and increase the risk of

short- term and long-term complications (Tully et al., 2008). The DASS-21 has 21 questions that index the level of depression, anxiety and stress an individual has experienced in the pre- ceding week. It is a valid and reliable measure that is frequently used in clinical practice and research alike (Henry & Crawford, 2005).

Social Relationships and Support (2 x 4-item scales; 3 minutes) - There is a vast epidemiological and medical evidence base showing the important role that social connectedness with others plays in health and recovery (Holt-Lunstad et al., 2010; Marmot, 2005;). Recent evidence shows that the nature of social participation with individuals and groups of others can make differential contributions to these outcomes. The social support measures we propose are those that been used more extensively in previous research to address the issues of social process in a range different clinical populations (e.g., Gleibs et al., 2011; Haslam et al., 2014; Jetten et al., 2010; Morton et al., 2015).

Loneliness Scale (3 minutes) - People who are less connected socially also experience higher perceived loneliness and social isolation. To capture this, the study incorporates a standardised 3-item Loneliness scale (Hughes et al., 2004) comprising items from the well-validated UCLA Loneliness scale (Russell et al., 1980).

Total expected time for all cognitive assessment tools (including Pain 7.3 below): 45-60 minutes. All neuropsychological tests will be given in a counterbalanced order; with four different packages, randomly assigned at the four time points comprising the alternate versions of specific tests to manage practice effects.

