1 CLINICAL INVESTIGATION PLAN SUMMARY – PART ONE

TITLE	Prediction of post-operative cognitive decline following shoulder surgery in the beach chair position: the value of cerebral oximetry.
INVESTIGATORS	Principal: Associate [name], [name], [name], [name] Associate: [name], [name], [name], [name], [name]
OBJECTIVES	Primary aim: To examine the relationship between cerebral desaturation during shoulder surgery in the beach chair position, and post –operative cognitive decline. Secondary aims: 1. To determine the variation in cerebral oxygenation recorded using simultaneous application of the INVOS™ and FORE-SIGHT® oximeters, during shoulder surgery in the beach chair position. 2. Assess the relationship between cerebral oxygen desaturation and mean arterial pressure, incidence of nausea / vomiting, duration of hospital stay, BMI, hypertension and adverse events.
STUDY DESIGN	A prospective cohort study.
SITES	Brisbane Private Hospital.
NUMBER OF SUBJECTS	Approximately 200 participants will be recruited to this study.
TARGET POPULATION	Participants will be adults who require shoulder surgery in the beach chair position.
LENGTH OF CLINICAL INVESTIGATION	It is anticipated that this study will require 27 months from commencement of recruitment to final data collection phases (24 month recruitment period). The primary end point of the study will be 3 months post-surgery. Participants will be assessed 1 day prior to surgery (baseline), at day 1 post-surgery (early), between 10 & 14 days (mid), at 1 month (late) and at 3 months post –surgery (late).
OUTCOMES	Primary Post- operative cognitive decline will be defined as a drop of 1 standard deviation or more from baseline on 2 or more neuropsychological indices (Tournay-Jette et al., 2011). The following neuropsychological tests will be used; 
• Logical memory test• Trail making test: Delis-Kaplan Executive Function System• Single letter verbal fluency• Stroop test: Victoria’s version• List Learning: Rey Auditory Verbal Learning Test• Letter-Number Sequencing (from Wechsler Adult Intelligence Scale, 4th edition).

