6.1 STUDY INTERVENTIONS

Following recruitment to the study participants will be booked for surgery. An initial assessment (pre-operative screening test) will be conducted one day prior to surgery. Demographic information will be collected and the initial cognitive screen will be conducted at this assessment. Cognitive assessment will then be repeated at day 1, 10 days post-surgery and at one month and 3 months post-surgery. These time points coincide with standard follow-up intervals post shoulder surgery. Minor changes in the timing of these assessments will be made if necessary to accommodate pre and post-operative surgery schedules.

The intra- operative procedure will be as follows;

1. The patient's bed will be inclined between 30-70 degrees, with the angle being measured by an inclinometer.
2. The anaesthetic and surgical procedure will continue as usual whilst the oximeters record cerebral oxygenation.
3. Any CDE will be recorded on the data collection sheet. Additionally, a digital record will be obtained of mean arterial pressure and also oxygenation from the oximeters until surgery is complete and the patient has regained consciousness. This will allow more detailed analysis by the statistician.
4. Intraoperative drug administration data will be recorded on the data collection sheet (24.4). This will allow for analysis of potential confounding effects.
5. The type of surgical procedure and the duration of surgery will be recorded (24.4) to again reduce further confounding affects.
6. Any variations from the usual surgical/anaesthetic protocol or adverse events will be recorded on the data collection form (24.4).
7. Post-operative analgesia data will be recorded in the data collection form (24.4).

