7 DATA COLLECTION

7.1 DATA COLLECTION INTERVALS

Data Collection Interval	Review Method
Baseline (approx. 24 hours prior to surgery)	In person at the clinic
Day 1	In person on the ward
Between 10 and 14 days	In person at the clinic
1 month	In person at the clinic
3 months	In person at the clinic

Data will be collected by an independent assessor who is not involved in the provision of treatment. These data collection points have been chosen to assess both the immediate and longer term effects of cerebral desaturation on cognitive function.

The follow-up period for this study is 3 months. Assessment of cognitive function will be conducted 1 day pre-operatively and as part of routine follow-up appointments at approximately 1 day and 10 days post-op, 1 month and 3 months. In this way we hope to maximise study retention by avoiding the necessity for participants to return for additional appointments beyond those required for normal care.

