7.2.3 DATA COLLECTION FORMS FOR PRIMARY AND SECONDARY HYPOTHESES

Primary and secondary outcomes will be recorded for each participant on their data collection form. This form will include demographic, clinical and outcome data (24.4). The primary outcome to be measured is the incidence of Post-operative Cognitive Decline. This has been defined as a drop of 1 standard deviation or more from baseline on 2 or more of the neuropsychological indices included. The secondary outcome to be measured is the incidence of cerebral desaturation as well as the importance of other key clinical variables (e.g. blood pressure, nausea, body fat etc).

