8 OUTCOME MEASURES

8.1 COGNITIVE ASSESSMENT TOOLS

8.1.1 NEUROPSYCHOLOGICAL TESTS

Logical Memory (5 minutes) - impairment in perceptions of and/or psychometrically determined, immediate and delayed recall and recognition memory following surgery has been frequently noted in research examining POCD (Krenk et al., 2010; Salazar et al., 2013). Commonly used psychometrically viable tests are prose story memory recall and recognition tests. The prose story is administered at the beginning of the session and the immediate recall occurs straight after. Delayed recall for the story occurs after 20-30 minutes. The test-retest reliability, construct and convergent validity of this test has been proven time again, commonly rendering an adequate to good coefficient (Sullivan, 2005).

Trails: Delis-Kaplan Executive Function System (10 minutes) - The D-KEFS was designed to detect even mild forms of executive dysfunction (Strauss et al., 2006). Executive dysfunction has been inadvertently linked with significant post-operative cognitive declines following surgery (Krenk, et. al., 2010). The D-KEFs Trails subtest has four trials; visual scanning, number sequencing, letter sequencing and letter number sequencing. The internal and test-retest reliability, and convergent and predictive validity of the D-KEFS is consistently adequate to high, and this subtest in particular renders a good to high coefficient (Strauss, et al., 2006).

Single Letter Verbal Fluency (1 minute) - Performance on brief verbal fluency tasks have been found to change pre- to post- surgery following cerebral desaturation events (Salazar et al., 2013). Aside from being a suitable assessment of both premorbid and current intellectual performance, tasks of verbal fluency examine spontaneous production of language and verbal associations. The task requires the individual to spontaneously generate a list of words in 60 seconds, where the words cannot be name of places, people or other proper nouns. A one-letter task is administered per package and has been found to be as valid as a three-letter fluency task (i.e. FAS or PGH;

Strauss, et al., 2006). Verbal fluency tasks have been found to have high internal and test-retest reliability and adequate to high content, construct and predictive validity (Strauss, et al., 2006).

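### Section 8.1.2 assigns four test packages to four time points, but five cognitive sessions are scheduled: a package repeats or the baseline form is undefined, and nothing stops baseline and 3 months from sharing one

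*Protocol*

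**What the plan says.** - **Packages.** Section 8.1.2 closes by saying that the neuropsychological tests are counterbalanced, "with four different packages, randomly assigned at the four time points comprising the alternate versions of specific tests to manage practice effects".
- **Package content.** Section 8.1.1 ties verbal fluency to the package: "A one-letter task is administered per package". The source cited for the story test is, by its title, about alternate prose forms. The protocol does not list which other tests vary by package.
- **Schedule.** The section 1 summary reads "Participants will be assessed 1 day prior to surgery (baseline), at day 1 post-surgery (early), between 10 & 14 days (mid", and the same sentence goes on to 1 month and 3 months. Section 6.1 says of the pre-operative visit that "the initial cognitive screen will be conducted at this assessment", and then: "Cognitive assessment will then be repeated at day 1, 10 days post-surgery and at one month and 3 months post-surgery". Section 7.1 agrees: "Assessment of cognitive function will be conducted 1 day pre-operatively and as part of routine follow-up appointments", at the same four post-operative times.
- **Outcome.** POCD is "defined as a drop of 1 standard deviation or more from baseline on 2 or more of the neuropsychological indices included" (section 7.2.3). Section 1 adds: "The primary end point of the study will be 3 months post-surgery".

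**The concern.** The package rule exists to control practice effects in a change-from-baseline outcome, yet its count does not match the schedule. Two readings are open.

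1. The four packages serve all five sessions, so at least one must be used twice.
2. They serve the four post-operative sessions only, so the baseline form is undefined. If baseline takes one of the four, that package returns at some later visit. If it takes a separate form, nothing repeats, but no such form is described.

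Under either reading, no rule keeps baseline and 3 months apart. A participant who meets the same fluency letter or story at both may gain from having seen it. That gain offsets true decline in the score that classifies POCD, which could lower the POCD rate and shrink the contrast between participants with and without a cerebral desaturation event (CDE).

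**Working it through.** **Step 1: count.** Section 8.1.2 has 4 packages at 4 time points. Sections 1, 6.1 and 7.1 each have 1 baseline + 4 post-operative = 5 sessions. Five sessions served by four packages force at least one repeat.

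**Step 2: chance that baseline and 3 months share a package.** The protocol states no scheme, so the plausible ones were enumerated.

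| Scheme | Sequences | Sharing | Of 193 |
|---|---|---|---|
| Baseline has its own form | n/a | 0% | 0 |
| All four used, one repeat at random | 10 session pairs × 4! = 240 | 24/240 = 10% | 19 |
| Same, no back-to-back repeat | 6 pairs × 4! = 144 | 24/144 = 16.7% | 32 |
| Four permuted over four sessions, the remaining session (baseline or 3 months) drawn at random | 4! × 4 = 96 | 24/96 = 25% | 48 |
| Independent draw at each session | 4^5 = 1024 | 256/1024 = 25% | 48 |

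**Step 3: the plan's own sample size.** Section 10.1 gives 62% without desaturation, POCD 29% against 50%, alpha 0.05, power 80% and 193 participants. Two-sided testing is assumed here. The two-proportion formula needs 178 without continuity correction and 197 with it, so 193 lies between. Power at 193:

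- Group sizes: 193 × 0.62 = 119.66 and 193 × 0.38 = 73.34. Pooled rate: 0.62 × 0.29 + 0.38 × 0.50 = 0.3698.
- Null SE = sqrt(0.3698 × 0.6302 × (1/119.66 + 1/73.34)) = 0.0716. Alternative SE = sqrt(0.29 × 0.71/119.66 + 0.25/73.34) = 0.0716.
- Uncorrected: Φ((0.21 − 1.96 × 0.0716)/0.0716) = 83.5%. With continuity correction (difference reduced by 0.011): 79.4%.

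The protocol's stated power is 80%. The 83.5% serves below only as the reference for losses under the same formula.

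**Step 4: possible size of the effect.** None of these inputs is in the protocol; all are assumptions:

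- six indices, one per listed test, with POCD as at least two drops of at least 1 baseline SD;
- normal change scores with SD sqrt(2(1 − r)), r = 0.7, 0.8 or 0.9, and correlation between changes of 0 or 0.3;
- mean change set to give 29% and 50% without any gain;
- a repeat-form gain of 0.3 or 0.5 SD on package-specific tests, only where baseline and 3 months share.

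The contrast is linear in the sharing fraction f: D(f) = 21 − f × (21 − D1), where D1 is the contrast if everyone shared. By numerical integration, D1 is 18.7-20.4 points for one test and 11.8-18.9 for three. For example, at f = 0.25 with three tests the lower end is 21 − 0.25 × (21 − 11.8) = 18.7.

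| Sharing | Tests affected | Contrast (points) | Power at 193 (83.5% if none) |
|---|---|---|---|
| 25% | 1 | 20.4-20.9 | 82.1-83.2% |
| 25% | 2 | 19.7-20.7 | 80.1-82.9% |
| 25% | 3 | 18.7-20.5 | 77.2-82.5% |
| 10% | 3 | 20.1-20.8 | 81.0-83.1% |

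With a gain of 0.1 SD, 25% sharing and three tests, power is 82.6-83.2%. With no gain there is no loss.

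**The case against.** The strongest answer is that section 6.1 lists exactly four occasions on which cognitive assessment is repeated. Four packages over those four visits is naturally one each, and no repeat is forced if baseline has its own form. On that reading the only gap is which form baseline uses. A schedule might also be printed on the cognitive pages of form 24.4, which are not in the text at hand. This stands as far as it goes: a repeat is not certain. It does not remove the mismatch, because the outcome needs the battery at baseline and no baseline form is named. Section 8.1.2 would still have to agree with the session lists.

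The word screen in section 6.1 might suggest that baseline is only a brief test. Section 7.1 and the change-from-baseline definition rule that out.

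The harm is also fairly challenged. The assumed gain has no source in the protocol, and it would have to survive three months and three intervening sessions. Package variation is explicit for one test only. Power drops below 80% in the table only with 25% sharing, three affected tests and assumptions towards the unfavourable end. All of this stands.

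**Conclusion.** The count mismatch is certain: four packages and four time points against five sessions. It leaves the form pairing behind the primary outcome uncontrolled, with 0% to 25% of participants sharing a package at baseline and 3 months. The likely cost is small: mostly 0 to 3 points of power, reaching about 6 (83.5 − 77.2 = 6.3) only with 25% sharing and three package-specific tests. Those figures rest on the assumed gain and the model above, not on the protocol.

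A reader might infer more, but the documents do not support it:

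- **That a repeat at the primary comparison is built in.** It is only not prevented.
- **That the CDE-POCD association would be falsely created.** Randomly assigned packages should be unrelated to CDE, so the expected effect is dilution.
- **That the study is underpowered because of this.** The modelled losses are mostly slight, and the stated power is 80%.

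Severity is minor to moderate. High confidence applies to the count only.

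**What to change.** Correct section 8.1.2 to five sessions including baseline. Randomise the order of the four packages under one constraint: baseline and 3 months never share one. Of the 240 orders that use all four, 9 pairs × 24 = 216 qualify. Let the one unavoidable repeat fall at random among the other session pairs. Record the package at each session so that it can be a factor in the analysis of change.

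**Cost.** A corrected sentence, an allocation list and one recorded item, which form 24.4 may already hold. There is no extra testing and no change to the POCD definition or the 193.

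**Downside.** The repeat moves rather than disappears. Each earlier post-operative visit shares the baseline package in 24/216 = 11% of participants. At 3 months, 72/216 = 33% meet a package already used at an intermediate visit, against none who meet their baseline package. If that exposure left the same gain, D(1/3) with three tests would be 17.9-20.3 points, so recording the package matters. A stricter list with a new package at 3 months is possible (6 pairs × 24 = 144 orders), but half of participants would then have their repeat at 1 month.

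**Alternatives to treat with care.**

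- A fifth form is an option only if it exists and is rotated with the others. A fixed baseline-only form would put any difference in form difficulty into every change score. In the model above with independent indices, an assumed 0.3 SD difference on three tests moves the 29% rate to about 15-19% or 44-56%.
- A fixed pattern such as A-B-C-B-D protects 3 months but gives everyone the repeat at 1 month. If 29% and 50% also held there, the three-test contrast at that visit would be 11.8-18.9 points.

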8.2 CEREBRAL DESATURATION

The incidence of cerebral desaturation events using both the INVOS™ and FORE-SIGHT® machines will be recorded on the data collection form. Cerebral desaturation will be defined as a decrease in rSO₂ greater than, or equal to 20% from baseline or a fall below 50% absolute (after Murphy et al., 2010; Salazar et al., 2013).

We will use data capture software that will simultaneously provide a record from which we can determine the number, severity and length of CDEs from both INVOS and Foresight sensors plus MAP. Subanalyses performed on these may attempt to ascertain whether or not any of these factors are important.

8.3 PAIN

Pain is a common occurrence with any injury and a highly predominant outcome post-surgery (Mitchell, Adebajo, Hay, & Carr, 2005). To capture this; the study will incorporate a validated, analogue global pain scale (0-100; Williamson & Hoggart, 2005). Each increment is a Likert-type scale of 0-100, where “0” is no pain, “50” is moderate pain and “100” is the worst imaginable pain. The participant will be asked to label which increment at which their current pain is falling.

8.4 ADVERSE EVENTS

Any adverse events arising during the trial will be closely monitored and followed up until the resolution of symptoms. These will be checked at each assessment stage and recorded on the data collection form (24.4).

9 CONFIDENTIALITY

Information about study subjects will be kept confidential and managed accordingly to the requirement of Human Research as determined by the NHMRC, and the local ethics review board, in this case, the Bellberry Human Research Ethics Committee.

All raw data forms will be kept in an individually identifiable format. The data collection forms and the master participant list with patient names; contact details and a study specific number will be kept in a secure lockable cabinet at the Brisbane Hand and Upper Limb Research Institute. All data will be transcribed in a re-identifiable format and analysed and reported in a non-identifiable format.

10 DATA ANALYSIS

Data will be transcribed from the participants data collection forms into excel spreadsheets in a re-identifiable format. Analysis will be performed with the assistance of a statistician and the statistical package used will be SPSS.

10.1 STATISTICAL METHODS

Baseline demographic and clinical data will be examined using descriptive statistics (means, standard deviations [SDs], and percentages). Dropouts will be compared to those who complete the study. For initial data screening, descriptive statistics (means, standard deviations [SDs], and percentages) will be completed for all predictor and outcome variables. Based on the findings of de Tournay - Jette et al. (2011), we assume that 62% of patients will not experience desaturation, and that the probability of postoperative cognitive dysfunction in these patients is 29%. To observe an increased risk of cognitive dysfunction of 1.75 times in patients who experienced desaturation (i.e. to 50%) we will be required to collect postoperative data on 193 participants, assuming $\alpha=0.05$ and $\text{power}=80\%$. For the secondary outcome, which is the concordance between the INVOS™ 5100 and FORE-SIGHT® devices during shoulder surgery, the agreement between these pairs of observations will be assessed using intra-class correlation (ICC 3,1) (Portney & Watkins, 1993).

A number of statistical analyses will be used to explore the relationship between CDE and other study variables to allow for use of continuous and categorical data (e.g. linear & logistic regression). With an anticipated sample size of 200 this should provide adequate numbers for our analysis (Portney & Watkins, 1993). Prior to the use of a regression analysis, exploratory bivariate analyses (e.g. correlation, chi square, one-way ANOVA) will be conducted among all predictor variables to identify multi-collinearity. Bivariate analyses between each predictor and outcome variable will then be conducted. Significant predictor variables identified from bivariate analyses will be entered into the regression model. A process of backward elimination will then be used to identify the best model considering main effects and two-way interactions at $p \leq 0.05$. Data analysis will be conducted using SSPS version 23. Any complication rates will be reported in terms of frequency and analysed. The potential contribution of type of surgery, the length of surgery and the nature of the anaesthetic agents

used are recorded as standard practice and will be included in analyses to assess whether or not they represent confounding factors. The final multivariable model will include the main effects of interest and variables identified as potential confounders.

The type and duration of anaesthesia is being recorded (see 15.4). Although the choices of anaesthetic medications and techniques may affect the incidences of cerebral desaturation event, they do not have any impact on correlating cerebral desaturation events, should they occur, and the postoperative metrics we are seeking to measure other than the secondary outcomes of pain and postoperative nausea and vomiting. By recording these additional data sets we will seek to ascertain any confounding effects they may have on the pain and postoperative nausea and vomiting but they will not be relevant to cerebral desaturation events since we are looking at the effects of the cerebral desaturation events rather than their incidence.

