	
Secondary Frequency of cerebral desaturation events (CDE) measured (INVOS™ vs FORE-SIGHT®). Cerebral desaturation will be defined as a decrease in rSO2 greater than, or equal to 20% from baseline or a fall below 50% absolute (after Murphy et al., 2010; Salazar et al., 2013). Variables associated with this outcome include:
 
 • Mean Arterial Pressure (mmHg) • BMI • Hypertension • Nausea and Vomiting – within 48 hours • Duration of hospital stay • Adverse Events
--	---

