Monitoring cerebral oxygenation in the BCP is an area of evolving attitudes in regards to standard of care. There are many hospitals in Australia who have now adopted cerebral oximetry as a standard of care for monitoring patients in the beach chair position. It is the feeling of all of the surgeons involved in the investigation that in fact, cerebral oxygenation monitoring is part of an adequate standard of care for patients in the beach chair position and it is routinely utilised currently in all beach chair position surgeries. It is not expected that there will be any significant alteration to operative time by placing two oxygen monitors and there is certainly no risk to the surgeon, anaesthetist or the nursing team. Data is recorded using monitors that output the data digitally and all of the data will be compared using standard timestamp methods so that they can be directly compared. The oximetry and MAP data will be simultaneously digitally recorded for the research data collection and analyses.

In conclusion, the relationship between shoulder surgery in the BCP and cerebral oxygenation is suggestive and requires further investigation. In addition, factors associated with cerebral desaturation and the incidence of POCD are not well understood. The value of cerebral oximetry in predicting CDE and POCD remains unclear. Further research in these areas is indicated and the proposed study aims to address the issues raised here.

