3.4 RESEARCH QUESTION

There are three research questions correlating with the three research aims;

- (i) Is cerebral desaturation during shoulder surgery associated with POCD?
- (ii) Do the FORE-SIGHT® and INVOS™ 5100 devices vary in their measurement of cerebral oxygenation during shoulder surgery in the BCP?

- (iii) Is there a relationship between cerebral desaturation events during shoulder surgery in the BCP and variables including mean arterial blood pressure, post-operative nausea/vomiting, length of hospital stay, BMI, hypertension and any adverse events?

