3.5 NULL HYPOTHESES

The three null hypotheses are;

- (i) Cerebral desaturation as measured using cerebral oximetry is not related to POCD after shoulder surgery in the BCP.
- (ii) There is no significant difference between the INVOS™ 5100 and the FORE-SIGHT® monitors assessment of cerebral oxygenation during shoulder surgery in the BCP.
- (iii) There is no relationship between cerebral desaturation events during shoulder surgery in the BCP and variables including mean arterial blood pressure, the frequency of post-operative nausea/vomiting, length of hospital stay, BMI, hypertension and any adverse events.

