3.6 PRIMARY HYPOTHESES

The primary research hypotheses are;

- (i) Cerebral desaturation events during surgery in the BCP will be related to POCD.
- (ii) The INVOS™ 5100 and the FORE-SIGHT® monitors will show no significant difference in their ability to measure cerebral oxygenation.
- (iii) Cerebral desaturation events experienced during shoulder surgery in the BCP are related to a drop in mean arterial blood pressure, an increased likelihood of post-operative nausea and vomiting, greater length of hospital stay, a higher BMI, hypertension and greater frequency of adverse events.

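### ICC(3,1), the only agreement statistic named for the two oximeters, cannot show a constant offset between them, and hypothesis 3.6(ii) restates its own null without a margin

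*Protocol*

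**What the plan says.** Section 10.1 introduces the device comparison with "For the secondary outcome, which is the concordance between the INVOS™ 5100 and FORE-SIGHT® devices during shoulder surgery" and then states that "the agreement between these pairs of observations will be assessed using intra-class correlation (ICC 3,1". It names no other statistic for agreement between the devices.

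The aim this serves is set out in three places:

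- Section 3.4, question (ii), asks whether the two "devices vary in their measurement of cerebral oxygenation during shoulder surgery in the BCP".
- Section 3.5, null (ii), denies a significant difference between the two "monitors assessment of cerebral oxygenation during shoulder surgery in the BCP".
- Section 3.6, research hypothesis (ii), predicts that the two "monitors will show no significant difference in their ability to measure cerebral oxygenation".

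Two other parts of the protocol bear on the point. Section 8.2 defines cerebral desaturation as a drop of at least "20% from baseline or a fall below 50% absolute". The summary in section 1 lists "Frequency of cerebral desaturation events (CDE) measured" on INVOS versus FORE-SIGHT as a secondary outcome.

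**The concern.** There are two faults.

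**The coefficient.** A question about whether two monitors differ covers two things: whether they rank patients alike, and whether one reads higher than the other. ICC(3,1), as conventionally defined, answers only the first. Section 10.1 nevertheless calls the result agreement.

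**The hypothesis.** In section 3.6, items (i) and (iii) contradict their nulls in 3.5. Item (ii) repeats its null. Failing to reject a null does not confirm it, and no margin is given that would turn the claim into a testable one of equivalence.

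Together these allow a high ICC(3,1) to be reported as device agreement, in line with 3.6(ii), when one monitor reads systematically higher. That coefficient could then contradict the device means and the desaturation counts printed beside it.

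**Working it through.** The protocol gives no figure for the device comparison that could be reproduced. The 193 participants in section 10.1 belong to the primary comparison and play no part here.

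**Step 1: the algebra.** For two devices on n patients, write BMS for the between-patient mean square, DMS for the between-device mean square and EMS for the error mean square.

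- ICC(3,1) = (BMS − EMS) / (BMS + EMS)
- Absolute-agreement ICC = (BMS − EMS) / (BMS + EMS + 2(DMS − EMS)/n)

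A constant added to one device changes DMS only. DMS is absent from the first formula, so ICC(3,1) does not move. This needs no assumed values.

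**Step 2: the size.** With between-patient SD sp, device error SD se and constant offset d, the expected values are:

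- ICC(3,1) = sp² / (sp² + se²)
- Absolute-agreement ICC = sp² / (sp² + se² + d²/2)

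The documents give none of sp, se or d, so all three are assumptions. For sp = 8 and se = 4:

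| Offset d (points) | ICC(3,1) | Absolute agreement |
|---|---|---|
| 0 | 64/80 = 0.80 | 64/80 = 0.80 |
| 5 | 64/80 = 0.80 | 64/92.5 = 0.69 |
| 10 | 64/80 = 0.80 | 64/130 = 0.49 |

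Over sp from 6 to 10 and se from 3 to 5, the extremes are:

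- ICC(3,1): 36/61 = 0.59 to 100/109 = 0.92, whatever the offset.
- Absolute agreement at 5 points: 36/73.5 = 0.49 to 100/121.5 = 0.82.
- Absolute agreement at 10 points: 36/111 = 0.32 to 100/159 = 0.63.

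A simulation of 1000 sets of 200 pairs (sp = 8, se = 4) agrees. ICC(3,1) was identical within every set at all three offsets (mean 0.798), and absolute agreement averaged 0.798, 0.690 and 0.490.

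**Step 3: whether an offset matters under the protocol's own event rule.** Reading the 20% limb of section 8.2 as a relative fall, the fall needed for an event is the smaller of 0.2 × baseline and baseline − 50. The two limbs meet at 50/0.8 = 62.5. With an assumed 5-point offset:

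- A patient at 58 on one device needs a fall of just over 8 points (0.2 × 58 = 11.6 is larger). At 63 on the other device the same patient needs 12.6 (63 − 50 = 13 is larger).
- A patient at 65 and 70 needs falls of 13 and 14 points.

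An offset therefore changes event classification mainly in patients with a low baseline.

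**Step 4: the hypotheses.** Null 3.5(ii) and hypothesis 3.6(ii) differ in wording (the monitors' assessment of oxygenation, against their ability to measure it) but not in substance. Both assert no significant difference. No margin is attached to either.

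**The case against.** The strongest reply has four parts.

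- **The label may not mean consistency.** A two-way mixed, single-measure ICC can be run with an absolute-agreement definition, and section 10.1 speaks of agreement and concordance. This is possible. But the label conventionally denotes consistency, and nothing in the protocol says otherwise. If absolute agreement is meant, the text still needs correcting.
- **An offset would be seen elsewhere.** Section 10.1 plans means and SDs for all predictor and outcome variables, and desaturation frequency by device is an outcome in its own right. This stands and limits the harm. However, the means are described as initial data screening, and neither result alters what the named coefficient would be taken to show.
- **The offsets are hypothetical.** This also stands. The documents give no offset, and the one beach-chair comparison of these monitors described in section 2 is reported as finding no significant difference. Only the invariance is established; the sizes are illustrative.
- **A statistical analysis plan could supply the rest.** The absence of bias estimates or limits of agreement carries no weight here for that reason. But the protocol itself fixes the coefficient and the hypothesis, so such a plan would have to depart from both.

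It is also fair to say that expecting no difference is a legitimate prediction. The fault lies in framing it as non-significance without a margin, and changing the ICC alone would not cure that.

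**Conclusion.** Both faults hold. That ICC(3,1) in its standard form is blind to a constant device offset is algebraic. How far it overstates agreement depends on assumed values: 0.80 against 0.69 at 5 points and 0.49 at 10 points for SDs of 8 and 4, with the ranges above. Hypothesis 3.6(ii) cannot be supported either by a non-significant difference or by a high ICC(3,1).

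This should be fixed, but its reach is limited. It concerns secondary aim (ii) only. The primary aim, the sample size and the data collected are untouched.

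**What to change.** In section 10.1, replace ICC(3,1) with an absolute-agreement ICC. Alongside it, report the mean between-device difference with its 95% CI, and limits of agreement that allow for repeated readings within a patient. If ICC(3,1) is kept as well, call it consistency. Because an absolute-agreement ICC also depends on the spread between patients, the bias and limits should carry the interpretation.

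Reword 3.6(ii) either as an estimation aim (how large the between-device difference is) or as equivalence within a justified margin stated in advance.

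No new data are needed: section 2 already plans simultaneous digital recording and says "all of the data will be compared using standard timestamp methods so that they can be directly compared". The cost is a protocol edit, a modest extra analysis and, if equivalence is chosen, the work of justifying a margin.

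Precision should be ample. Take 200 patients, one pair each and an assumed error SD of 3 to 5, so that the SD of a difference is √2 × 3 = 4.2 to √2 × 5 = 7.1:

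- 95% CI half-width for the bias: 1.96 × SD/√200 = 0.6 to 1.0 points.
- Limits of agreement: bias ± 1.96 × SD = ± 8.3 to ± 13.9 points, each limit with a 95% CI half-width of 1.96 × SD × √(3/200) = 1.0 to 1.7 points.
- Smallest equivalence margin with 90% power at a true difference of zero: (1.645 + 1.645) × SD/√200 = 1.0 to 1.6 points.

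Oximetry is recorded during surgery, so the 30% loss to follow-up in section 5.5 does not reduce this number. Participants who do not go on to surgery (section 5.3.3) would reduce it.
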